Reproductive Health Survivorship Care Plan Trial Protocol

NCT02667626 February 1, 2016

Design of a randomized controlled trial on the efficacy of a reproductive health survivorship care plan in young breast cancer survivors

Introduction

There are nearly 3.5 million breast cancer survivors in the United States, with 19% of new cases occurring in women age 45 and younger. Most young breast cancer survivors (YBCS) undergo chemotherapy and/or endocrine therapy, treatments that can impair ovarian function and result in significant reproductive health issues. These include hot flashes, infertility, sexual dysfunction, and limited contraception options, which negatively impact quality of life in survivorship. Evidence-based clinical strategies to manage these late effects have been identified, but have limited dissemination among YBCS and their healthcare providers (HCPs), resulting in unmet informational needs among YBCS on reproductive health [3].

Breast cancer survivors seek health information and advice from their HCPs and online. Information seeking in YBCS is associated with increased self-efficacy, satisfaction with treatment decisions, and improved quality of life [6,8]. Coupled to underinsurance, limited healthcare access and high mobility in YBCS, these information-seeking characteristics motivated us to develop a web-based intervention on reproductive health for YBCS and their HCPs.

In 2006, the Institute of Medicine recommended development of survivorship care plans (SCPs) to support the transition of care from cancer treatment to survivorship. SCPs aim to inform patients about the effects of cancer treatment, guide follow-up care, and improve care coordination. Internet accessible SCPs for breast cancer survivors have been developed, but contain limited reproductive health guidance. Randomized controlled trials on the efficacy of SCPs on patient-reported and health services outcomes have included YBCS, but none have focused on reproductive health.

The web-based Survivorship Care Plan in Reproductive Health (SCP-R) intervention was developed to address unmet informational and clinical management needs for hot flashes, fertility-related concerns, contraception, and sexual health in YBCS. Research findings, professional society guidelines and clinical expertise on these reproductive health issues were curated into screening and management strategies that will be delivered to YBCS and their HCPs via the SCP-R intervention. A web-based intervention and text message support were chosen to enhance intervention accessibility.

This report details the design, recruitment, and baseline characteristics of YBCS and HCP participants of the randomized controlled trial testing the efficacy of the SCP-R intervention on improving reproductive health in YBCS. We hypothesize that YBCS who receive the SCP-R intervention will be more likely to improve on at least one of four targeted reproductive health outcomes (hot flashes, fertility-related concerns, sexual health, and contraception) compared to waitlist controls.

Material and Methods

The SCP-R trial will test the efficacy of a 24-week, web-based educational intervention with text message support in improving reproductive health issues experienced by female YBCS.

Following online eligibility screening and consent, YBCS complete an enrollment questionnaire and undergo a 7-day run-in period for reporting daily hot flash frequency and severity via text messaging. Adherent participants are randomized in a 1:1 ratio to the intervention or waitlist control arm. Participants in the intervention arm receive access to the full web-based SCP-R intervention and reproductive health text message prompts, while participants in the waitlist control arm receive access to a list of curated web-based resources and study adherence text messages. All participants will be followed for 24 weeks, report daily hot flash frequency and severity via text messaging, and complete a 12-week and a final 24-week questionnaire.

To support YBCS-HCP interactions, one HCP is nominated by each YBCS participant to receive the same study materials as their patient. Following eligibility screening and consent online or by paper, HCP participants whose YBCS patients are randomized to the intervention arm will receive access the full web-based educational intervention; HCP participants whose YBCS patients are randomized to the waitlist control arm will receive access to the list of curated web-based resources. HCP participants will complete an enrollment and a 24-week questionnaire. The UC San Diego institutional review board approved all study procedures, and the trial was registered at clinicaltrials.gov (NCT02667626).

Intervention prototype development and refinement

In line with community-based participatory research [22], a stakeholder panel was formed to design and conduct the study. The panel was comprised of 2 YBCS advocates and 6 investigators with clinical and research expertise in reproductive health, primary care, breast oncology, health behavior and randomized trials. To develop the intervention, we conducted systematic reviews and searched professional medical society guidelines for evidence on managing hot flashes and sexual health, addressing contraception needs and predicting fertility potential [23–25]. Supplemented by clinical expertise and review of existing web-based resources from professional medical societies and cancer advocacy groups, these evidence- and guideline-based practices were summarized into the SCP-R prototype. SCP-R was designed to improve self-efficacy by providing both up-to-date evidence and actionable steps for symptom management. The multi-level intervention further promoted taking actionable steps by incorporating reinforcement from the YBCS' HCP.

Seven focus groups with 37 YBCS were conducted to refine the content and presentation of the SCP-R [26]. For the intervention arm, we initially planned to provide each participant with only the SCP-R sections relevant to her specific reproductive issue(s). Based on focus group feedback, we changed the intervention design to allow participants in the intervention arm to access to all SCP-R sections.

The final SCP-R intervention included four sections for each of the four planned reproductive health issue (hot flashes, fertility-related concerns, vaginal symptoms and contraception) and an additional fifth issue on genetic cancer risk. For each issue, the four sections included: 1) a 1- to 2-page SCP framed in a question and answer format; 2) a detailed summary of the systematic review results with hyperlinks to primary research articles; 3) a summary of clinical guidelines with hyperlinks; 4) a list of curated web-based resources. This content was programmed into the study website. The intervention arm will be able to access all 4 sections for all 5 issues (Appendix A); the waitlist control arm will only be able to access the list of curated web-based resources for all 5 issues.

Website and text messaging platforms

We collaborated with an experienced web architect to develop a HIPAA-compliant website that enabled online participant registration, consent, completion of questionnaires, automated randomization and access to group-specific intervention material, integration with MOSIO, a text messaging software, and pairing of YBCSs with their nominated HCPs. The web portal is programmed to send study gift cards and weekly reminders on incomplete tasks to YBCS and HCP participants.

The text messaging platform is programmed to push daily text messages to all YBCS participants to ascertain hot flash frequency and severity. Natural language processing is embedded to minimize variation in how participants provide hot flash responses. In addition, biweekly text messages with reproductive health prompts will be sent to YBCS participants in the intervention arm, while biweekly study adherence text messages will be sent to YBCS participants in the waitlist control arm. The text messaging platform supports opt out by participants and two-way text messaging capabilities between participants and study staff.

This web- and text message-based design supports streamlined YBCS screening, consent, follow-up, and data collection, enables geographically diverse recruitment and utilizes fewer resources compared to a traditional in-person RCTs. Daily hot flash text messages will provide near real-time data collection to minimize recall bias.

YBCS eligibility, recruitment, consent and enrollment

YBCS are eligible if they report experiencing at least one of the four targeted reproductive health issues: hot flashes (\geq 4 per day with \geq 1 at least moderate in severity), moderate to high pregnancy and/or fertility concerns (fertility or pregnancy subscale score >3 on the Reproductive Concerns After Cancer Scale), not using contraception or using a less effective method (barrier or fertility awareness methods, withdrawal, or spermicides), or vaginal atrophy symptoms (\geq 1 symptom of vaginal dryness, irritation, soreness or dyspareunia over the past 4 weeks reported as at least moderate in severity). Additional eligibility criteria include: ages 18-50 at study enrollment, diagnosed with stage 0-III breast cancer between ages 18-45, completed primary cancer treatment including surgery, chemotherapy and radiation, are not pregnant at enrollment, are able to read English and access the Internet, and are able to complete daily text message hot flash diaries.

YBCS are recruited from the following sources: (1) cancer advocacy organizations including the Young Survival Coalition, Susan G. Komen San Diego and Army of Women-a program by the [name] Research Foundation, (2) referrals from health care providers and patient advocates, (3) Research Match, (4) previous observational studies conducted by the investigators. Interested YBCS are directed to the study web portal to create a secure personal account, followed by online access to study description, screening for eligibility and consent.

Consented participants complete the enrollment questionnaire and undergo a 7-day daily hot flash text message run-in period. Participants receive two daily text messages prompting them to report the number of hot flashes and severity of each hot flash (mild, moderate, severe, or very severe) in the previous 24 hours. Participants with at least 70% adherence over 7 days are then randomized.

YBCS randomization

Computerized, blocked randomization with equal allocation to intervention and waitlist control arms was undertaken. Randomization is stratified by the four a priori reproductive health issues in order to

maintain balance between the intervention and waitlist control groups with regard to these factors. Fifteen unique strata were created based on possible combinations of experiencing one or more of the four late effects.

HCP eligibility, recruitment, consent, enrollment and procedures

At enrollment, each YBCS participant nominates a HCP with whom they wish to discuss reproductive health issues. Study staff contact nominated HCPs by email, phone and/or fax for study recruitment. After five contacts, non-responsive HCPs are mailed the study consent, enrollment questionnaire and their patient's SCP materials. Interested HCPs are directed to the study web portal to create a secure personal account, followed by online access to study description, screening for eligibility and consent. Consented HCP participants complete the enrollment questionnaire and are provided with access to their patient's intervention materials, i.e. full SCP-R or only curated web-based resource lists. HCPs will complete a 24-week questionnaire and may opt to complete all study procedures (consent, questionnaires) and access intervention materials in a paper format.

Blinding

Study staff and YBCS and HCP participants are blinded to treatment allocation. Automated computer allocation of participants into intervention or waitlist control arm within the study portal allow for study staff to be blinded to assignment. YBCS and HCP participants are informed about participant randomization in the trial but are not notified of assignment until they complete their final study tasks. YBCS and HCP participants assigned to the waitlist control arm will be able to access the full SCP-R materials following completion of their final study tasks. Although 3 HCPs were nominated by more than one YBCS participant, each HCP only had participants in the same study arm.

YBCS outcome measures

Hot flash frequency and severity over the prior 24 hours will be measured in each questionnaire and via daily via text messages using the following questions: "How many hot flashes have you had in the past 24 hours?" and "How many of your hot flashes in the past 24 hours would you categorize as mild, moderate, severe and/or very severe?" The hot flash score is calculated as the weighted sum of the number of hot flashes in each severity category multiplied by a severity-exclusive weight (1-mild, 2-moderate, 3-severe, 4-very severe). For the primary analysis, a decrease of 50% in the hot flash score will be defined as an improvement in hot flashes for the primary composite outcome. Secondary hot flash outcomes will include quality of life measured by the 29-item Menopause-specific Quality of Life (MENQOL) scale, confidence to talk with a HCP about hot flash management, plans to implement and implementation of a suggested tip from the intervention materials.

Fertility-related concerns will be measured with the Reproductive Concerns After Cancer Scale (RCAC), specifically fertility potential and pregnancy subscales. The RCAC is an 18-item multidimensional scale composed of 6 subscales (fertility potential, pregnancy, child's health, disclosure to partner of fertility status, personal health, acceptance of infertility) measuring reproductive health concerns of young adult female cancer survivors. The two subscales were chosen, because the SCP-R content addressed these constructs. Each subscale consists of 3 questions with response options ranging from 1 "Strongly disagree" to 3 "Neither agree nor

disagree" to 5 "Strongly agree". Scores for the fertility and pregnancy subscales will be calculated by averaging responses (range 1-5), scores > 3 indicating concern. For the primary analysis, scores \leq 3 in follow up will be considered an improvement in fertility-related concerns for the primary composite outcome. Secondary fertility-related outcomes will include the overall RCAC score, referral, consultation and treatment with a fertility specialist, pregnancy planning, and confidence to talk with a HCP about fertility-related concerns and plans to implement and implementation of suggestions from the fertility SCP.

Contraception outcomes will be analyzed in participants at risk of unintended pregnancy, defined as having a uterus and at least one ovary, sexually active in the 24 months prior to or during the study, ≤ 45 years old. For the primary analysis, use of highly effective birth control methods (intrauterine devices, female sterilization, male partner sterilization, combined hormonal contraception, progestin implants or injections) during follow up will be considered an improvement for the primary composite outcome. Secondary contraceptive outcomes will include confidence to talk with a HCP about contraception, plans to implement and implementation of suggestions from the contraception SCP.

Sexual health will be measured the Vaginal Atrophy Symptoms Score, a 4-item scale on vaginal dryness, soreness, irritation and dyspareunia experienced in the prior 4 weeks [29]. Each item has a 4-point Likert scale response (0-none, 1-mild, 2-moderate, 3-severe). The scale will be summarized by averaging responses, with higher scores indicating a greater level of vaginal atrophy. For the primary analysis, a decrease of 50% in the score will be defined as an improvement in vaginal symptoms for the primary composite outcome. Secondary outcomes included sexual desire, arousal, orgasm and pain via the 19-item Female Sexual Function Inventory (FSFI), confidence to talk with a HCP about vaginal symptoms and sexual health management, plans to implement and implementation of a suggested tip from the intervention materials.

HCP measures

HCP preparedness and confidence in talking to their patients about each of the four reproductive health issues will be measured. Each preparedness item had a 4-point Likert scale response (very unprepared, unprepared, prepared, and very prepared). Each confidence item had a 7-point Likert scale response (not at all confident, slightly confident, somewhat confident, moderately confident, quite confident, very confident, and extremely confident). Demographic, medical specialty, and experience and volume of breast cancer patients, and satisfaction with SCP materials will also be measured.

YBCS participant adherence and retention

We will deploy several approaches to motivate YBCS participants to complete the study. Participants will receive up to \$100 in Amazon gift cards for completing each of 3 questionnaires and daily hot flash text messages. Weekly, automated reminder emails to complete study tasks will be sent via the web platform. Telephone call and/or text message reminders will be undertaken for overdue tasks for up to 5 contacts. On hot flash text messages, daily reports will be generated to monitor responses and identify those who had not responded in \geq 3 consecutive days for study staff contact.

HCP participant adherence and retention

HCP participants will receive up to \$40 in Amazon gift cards for completing each of 2 questionnaires. Weekly, automated email reminders to complete study tasks and view their patient's SCP will be sent via the website platform. HCPs who opted to participate via paper materials will be contacted by telephone calls to their medical practice to confirm receipt and encourage completion overdue tasks for up to 5 contacts. If a final questionnaire is not received within two months of mailing, questionnaires will be resent.

Statistical Analysis

The primary analysis will be intent-to-treat. The primary composite outcome will be an improvement in at least one reproductive health issue over the 24 week study, defined as: $\geq 50\%$ improvement in enrollment hot flash score, $\geq 50\%$ improvement in enrollment vaginal atrophy symptom score, use of highly effective contraceptive methods (sterilization, long-acting reversible contraception, injectables, pills, patch or vaginal ring), and fertility and pregnancy concern subscale scores <3. Logistic regression models will be used to test for differences by intervention versus control arm; odds ratios with 95% confidence intervals for intervention effect will be reported.

To quantify intervention effects on each of the four reproductive health issues, we will also undertake secondary analyses to compare changes in each issue separately. As participant responses will be measured at enrollment, 12 and 24 weeks, we will compare each health issue outcome between the intervention and waitlist control groups using linear mixed effect models for the continuous outcomes (hot flash score, vaginal atrophy symptom score, fertility concerns score) and GEE models for binary outcomes (use of effective contraceptive method). Best linear unbiased predictors from the mixed models will also be used to impute missing outcomes for the primary composite outcome. Similar analysis will be conducted for secondary outcomes, which include additional YBCS-reported symptoms and actions, as well as healthcare provider preparedness and confidence.

Sample size

YBCS participants will be randomized into two arms: intervention and waitlist control. We will measure outcomes at enrollment, 12 weeks, and 24 weeks. Leveraging published data on hot flashes [31], we based sample-size calculations on detecting meaningful changes in hot flash frequency and score. With a sample size of 50/arm, there will be 80% power to detect a 0.57 effect-size between groups on hot flash score changes from baseline to 24 weeks based on a 2-sided t-test with alpha =0.05. This effect-size translates to a group difference of 1.2 hot flashes or 3 units in the hot flash score, if we assume the standard deviation of the change was 2 hot flashes or 5 score units per patient per day. Incorporating all the repeated measurements on each participant should ensure sufficient power to detect an even smaller effect size. In particular, assuming 2 post-randomization measures with autocorrelation 0.5, there is 80% power to detect a 0.44 effect size with 50 samples in each arm and 2-sided significance level 0.05.

Considering the composite primary outcome of improvement in at least 1 reproductive health issue, we have 80% power to detect a 27% group difference, e.g., 25% in the control arm and 52% in the treatment improve on at least one outcome. Given that some participants may have the same healthcare provider, we account for a clustering effect as follows: we assume as a worst-case scenario that on average 3 participants shared a provider, and that intraclass correlations (ICC) of the study outcomes due to a shared physician is 0.1. This results in a design

effect of 1.2, requiring us to inflate the sample-size by 20%. We further anticipate 20% sample size loss due to the run-in period prior to randomization, and an additional 20% drop-out rate. Hence, we aim to enroll 196 participants and randomize 157 to ensure sufficient power.

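### The contraception entry item and stratum carry no at-risk condition, the contraception outcome does, and the composite definition omits it again, so the scoring of some randomized women is undefined

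*Combined protocol and SAP*

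**What the plan says.** **Entry.** Under YBCS eligibility, recruitment, consent and enrollment, one issue is enough: "YBCS are eligible if they report experiencing at least one of the four targeted reproductive health issues". The contraception issue is "not using contraception or using a less effective method (barrier or fertility awareness methods, withdrawal, or spermicides". The general criteria include "ages 18-50 at study enrollment, diagnosed with stage 0-III breast cancer between ages 18-45" and not being pregnant. None of them concerns uterus, ovaries or sexual activity.

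**Randomization.** Under YBCS randomization, allocation is stratified on the same four issues: "Fifteen unique strata were created based on possible combinations of experiencing one or more of the four late effects".

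**Outcome.** Under YBCS outcome measures: "Contraception outcomes will be analyzed in participants at risk of unintended pregnancy, defined as having a uterus and at least one ovary", and further "sexually active in the 24 months prior to or during the study, ≤ 45 years old". The same paragraph defines what counts as contraception improvement for the primary composite.

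**Analysis.** Under Statistical Analysis: "The primary analysis will be intent-to-treat". The composite is improvement in at least one issue. Its contraception component is listed as use of a highly effective method, with no at-risk condition attached.

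**The concern.** Entry, stratification, outcome and analysis should all mean the same thing by having the contraception issue. Here they do not. A woman of 48, a woman after hysterectomy, or a woman who is not sexually active satisfies the entry item simply by using no contraception. The outcome section then removes her from the contraception analysis.

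If she also entered on hot flashes, fertility concerns or vaginal symptoms, she can still be scored on that issue. If contraception was her only entry issue, the outcome section leaves her no entry issue to score, while the Statistical Analysis section, read literally, still scores her on contraception. Nothing says which governs. The denominator of the primary endpoint is then left to a choice made at analysis, and such women may add little information about the intervention.

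There is a second problem. Sexual activity during follow-up can bring a woman into the at-risk set. That is post-randomization information, in a trial whose intervention includes sexual-health content, so membership could in principle be affected by arm.

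**Working it through.** **Step 1. Set the sections side by side.**

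| Condition | Entry item and stratum | Contraception outcome (YBCS outcome measures) | Composite component (Statistical Analysis) |
|---|---|---|---|
| Age | 18-50 | 45 or under | none stated |
| Uterus and an ovary | not required | required | none stated |
| Sexual activity | not required | required, in the 24 months before the study or during it | none stated |

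The fifteen strata are the 2^4 - 1 = 15 non-empty combinations of the four entry issues. One of them is contraception alone. The women with no entry issue left to score are the members of that stratum who are not at risk. The planned imputation from mixed models deals with missing outcomes, not with outcomes that do not apply, so it does not settle their status.

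**Step 2. Reproduce the plan's power.** Inputs from Sample size: 50 per arm and 25% v 52%. Two-sided alpha of 0.05 is stated there for the hot flash comparison and assumed here for the composite.

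Power = Φ[(d - 1.96 × se0) / se1], with se0 = √(2 p̄(1 - p̄)/n) and se1 = √([p1(1 - p1) + p2(1 - p2)]/n).

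- d = 0.27 and p̄ = 0.385
- se0 = √(2 × 0.385 × 0.615/50) = 0.0973
- se1 = √((0.1875 + 0.2496)/50) = 0.0935
- Power = Φ[(0.27 - 0.1907)/0.0935] = Φ(0.848) = 80.2%, against 80% stated.

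**Step 3. Illustrate the effect.** Let f be the share of each arm that cannot respond. The documents give no value, so f = 5%, 10% and 20% are assumptions. The planned rates are taken to hold in everyone else.

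- Counted as not improved: rates become 0.25(1 - f) and 0.52(1 - f), with n unchanged.
- Dropped: rates unchanged, n becomes n(1 - f).

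Two values of n are shown. The first is the plan's 50 per arm. The second is 157 × 0.8 / 2 = 62.8, taken as 62, which is the randomized target after 20% drop-out if no clustering allowance is needed.

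| f | Rates if not improved | Power, n = 50 | Power, n = 62 | Power if dropped, n = 50(1 - f) | Power if dropped, n = 62(1 - f) |
|---|---|---|---|---|---|
| 0 | 25.0% v 52.0% | 80.2% | 88% | 80.2% | 88% |
| 5% | 23.75% v 49.4% | 76.7% | 85% | 78.1% | 86% |
| 10% | 22.5% v 46.8% | 73.0% | 82% | 75.8% | 84% |
| 20% | 20.0% v 41.6% | 65.2% | 75% | 70.6% | 80% |

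**The case against.** The textual mismatch is hard to dispute. The case on the other side is about its consequences, and much of it stands.

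- **Certain non-responders.** A reader might infer that a woman who entered on contraception alone and is not at risk is bound to fail the composite. The documents do not support this, because they never say that only entry issues count. The entry thresholds leave room below them: she may have one to three hot flashes a day, or mild vaginal symptoms, and halve her score. The fertility component is an absolute follow-up score, which a woman without concerns could meet with no change at all. The Statistical Analysis section would also let her score on contraception. This does not rescue the plan. If the whole share f met the composite automatically, rates of 0.25(1 - f) + f and 0.52(1 - f) + f give power of 74.7%, 69.1% and 58.1% at 50 per arm for f = 5%, 10% and 20%.
- **Biased comparison.** A reader might infer that dropping these women biases the comparison. Age and anatomy at enrollment are fixed before allocation, so excluding on them alike in both arms changes the population studied but does not bias the contrast. Only the during-study part of the sexual-activity condition is open to that criticism.
- **Weakened stratification.** A reader might infer that balance suffers. Blocked randomization still balances the entry-defined issue, at-risk status is balanced in expectation within strata, and no stratum adjustment is specified that could be weakened. The effect is minor.
- **Size.** The share f covers only part of one stratum in fifteen and is unknown. The 50 per arm is the figure before inflation. The clustering allowance assumes on average three participants per provider, whereas the Blinding section reports only three providers nominated by more than one participant. At about 62 per arm, power falls below 80% only toward the top of the assumed range.

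The screening form is not in the documents, so how the portal applied the contraception item is unknown.

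**Conclusion.** The point holds as an inconsistency among the entry and stratification rule, the outcome definition and the composite definition, which no section resolves. Following the plan as written randomizes some women on an issue that its own outcome rule excludes. For those whose only entry issue is contraception, status in the primary analysis differs between two sections. At-risk membership also rests partly on post-randomization information.

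Its size cannot be computed from the documents. The illustrated losses (80% to 77-65% at 50 per arm, 88% to 85-75% at about 62 per arm) rest on an assumed 5-20% of women being unable to respond, on the planned rates holding in all others, and, for the second range, on negligible clustering. They show the order of the effect for a given share and are not a forecast. The documents do not show that these women must fail the composite, that excluding them on baseline characteristics biases the result, or that stratified balance is materially harmed. This is a correction worth making because it is cheap and removes a discretionary choice, not because the trial is shown to be underpowered.

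**What to change.** Reconcile the three places with one definition:

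1. Take the at-risk definition from YBCS outcome measures, assess it from enrollment data only, and delete the alternative that counts sexual activity during the study.
2. Apply it to the contraception entry item, to the contraception stratification factor, and to the contraception component of the composite under Statistical Analysis.
3. For women already randomized, keep all of them in the intent-to-treat set and state in advance how their composite is scored. Add a sensitivity analysis that excludes, by enrollment data, those with no scorable entry issue.

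The cost is a few items on the web screening form and some analysis-plan wording. Entry becomes slightly narrower, because women who would qualify only through non-use of contraception while not at risk would no longer be enrolled.

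### Healthcare providers recruited by mail receive their arm-specific materials together with the consent and enrollment questionnaire, so some enrollment scores may be given after exposure

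*Combined protocol and SAP*

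**What the plan says.** All references are to the combined protocol and SAP.

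The section on HCP eligibility, recruitment, consent, enrollment and procedures describes two routes into the study. For the usual route, "Consented HCP participants complete the enrollment questionnaire and are provided with access to their patient's intervention materials". For HCPs who have not replied, "After five contacts, non-responsive HCPs are mailed the study consent, enrollment questionnaire and their patient's SCP materials".

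The materials follow the patient's arm. Material and Methods states that "one HCP is nominated by each YBCS participant to receive the same study materials as their patient", and the HCP procedures section adds that HCPs "are provided with access to their patient's intervention materials, i.e. full SCP-R or only curated web-based resource lists".

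On measurement, Material and Methods says that "HCP participants will complete an enrollment and a 24-week questionnaire". The HCP measures section says that "HCP preparedness and confidence in talking to their patients about each of the four reproductive health issues will be measured", with a 4-point scale for preparedness and a 7-point scale for confidence.

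On analysis, the Statistical Analysis section describes mixed models and GEE for the patient outcomes and then says: "Similar analysis will be conducted for secondary outcomes, which include additional YBCS-reported symptoms and actions, as well as healthcare provider preparedness and confidence".

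**The concern.** HCPs have two measurement times, so the enrollment questionnaire is the only possible measure before exposure. The usual route keeps it ahead of the materials. The mailed route puts both in the same envelope and leaves the order to the HCP. Part of the SCP-R is a question-and-answer plan of 1 to 2 pages per issue, so reading it before filling in the form is quite possible.

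Two things are at stake. First, an intervention-arm HCP who reads the full SCP-R first may report an enrollment score that already contains part of the gain the trial wants to measure. Control HCPs who read first have seen only resource lists. If the early gain is larger with the full SCP-R, the arms differ at enrollment because of the intervention, and an analysis that subtracts or adjusts for the enrollment score removes part of the effect. Second, a mailed HCP can decide on consent after seeing content that differs by arm, so participation could differ by arm within this group.

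**Working it through.** **Step 1. Order of events by route.**

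| | Usual route | Mailed route |
|---|---|---|
| Consent | before access | same mailing as the materials |
| Enrollment questionnaire | named before access | same mailing as the materials |
| Instruction on order | follows from the sequence described | none |
| Order recorded | not needed | not planned |
| Flag in the analysis | not needed | not planned |

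The section on HCP adherence and retention does not fill the gap. Its paper-route follow-up consists of calls to confirm receipt and to encourage overdue tasks, and a second mailing of a late final questionnaire.

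**Step 2. Is there a plan figure to reproduce?** No. The Sample size section covers patients only. It gives no HCP sample size, target effect or power, and no count of HCPs expected to need the mailing.

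**Step 3. Effect on the contrast.** Define:

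- D: the true between-arm difference in HCP score at 24 weeks.
- f: the share of analysed HCPs who saw the materials before the enrollment questionnaire, taken as equal in the two arms.
- g_I and g_C: the immediate gain from the full SCP-R and from the resource lists.
- e = (g_I − g_C) / D: the share of the between-arm effect already present at the questionnaire.

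Without early exposure, the expected enrollment difference between arms is zero. With it:

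- Enrollment difference = f × (g_I − g_C) = f·e·D.
- Change-from-enrollment contrast = D − f·e·D = D × (1 − f·e).
- Contrast adjusted for the enrollment score with slope b = D − b·f·e·D = D × (1 − b·f·e). For b between 0 and 1, the loss is no larger than for change scores.
- 24-week contrast without the enrollment score = D, with no loss from this source.

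**Step 4. Numbers.** The documents give neither f nor e, so the values below are assumptions. Entries are the fraction of D kept by the change contrast, 1 − f·e.

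| f | e = 0.25 | e = 0.5 | e = 1 |
|---|---|---|---|
| 0 | 100% | 100% | 100% |
| 0.10 | 97.5% | 95% | 90% |
| 0.25 | 93.75% | 87.5% | 75% |
| 0.5 | 87.5% | 75% | 50% |

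For example, at f = 0.10 and e = 0.25, 1 − 0.10 × 0.25 = 0.975. At f = 0.5 and e = 0.5, 1 − 0.5 × 0.5 = 0.75.

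The formula assumes that reading early does not change the 24-week score. It does not cover differential consent, which could act in either direction and on any of the three contrasts.

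**The case against.** The strongest reply is that the affected group is narrow. An HCP must ignore five contacts, then consent, return the mailed questionnaire, and have read the materials before answering. HCPs who never consent supply no enrollment score. Nothing in the documents shows that f is large, and at f = 0 there is no loss. This stands, and it is why the size is left open.

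Control HCPs also receive something to read, so early gain is possible in both arms. A reader might infer that only the intervention arm is contaminated; the documents do not support that. Only the differential gain biases the contrast.

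The analysis is also less settled than it may look. The plan promises an analysis similar to the repeated-measures models, but does not say whether the HCP contrast is change from enrollment, an adjusted difference or the 24-week difference. The last would be free of the baseline bias. That the enrollment questionnaire carries the preparedness and confidence items is itself inferred from the two HCP questionnaires and the planned analysis.

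Finally, mailing the materials plausibly serves the design, which relies on reinforcement from the patient's HCP. That is a good reason to send them. It is no reason to leave the order open.

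**Conclusion.** The point holds as a possible, avoidable bias in secondary HCP outcomes. As written, the mailed route allows consent and enrollment scores to follow exposure to arm-specific materials, and nothing in the plan restores or records the order. If the full SCP-R produces the larger early gain, an enrollment-to-24-week or baseline-adjusted contrast is biased toward no effect. The size is unknown: under the assumed values the change contrast keeps between 97.5% and 50% of the true difference, and all of it if no HCP reads first.

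Two stronger conclusions are tempting and are not supported:

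- A reader might take the 50 per arm and effect size of 0.57 from the Sample size section and quote a loss of power for HCP outcomes. Those figures belong to the patients' hot flash score. With no HCP sample size or target effect, no HCP power loss can be stated.
- A reader might infer that the trial's main result is at risk. The primary composite uses patient outcomes only, and neither it nor its sample size depends on HCP enrollment scores. Nor can a baseline bias toward no effect by itself create a false positive HCP finding.

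Differential consent in the mailed group is likewise a possibility to monitor. The documents do not show that it occurs.

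**What to change.** - **Mailing.** Put the arm-specific materials in a sealed inner envelope marked to be opened only after the consent and enrollment questionnaire are completed. Ask the HCP to record the completion date and whether the materials were opened first. The date alone does not show the order.
- **Analysis.** Flag every mailed-route HCP. Prespecify a sensitivity analysis that either excludes these HCPs or compares 24-week scores by arm without the enrollment score. Excluding by route is preferable to excluding by reported order, because the route is set before the HCP opens the mailing.
- **Reporting.** Give HCP consent by arm for the mailed group.

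A model that constrains the enrollment means to be equal across arms is a tempting alternative. It relies on the balance that randomization provides, which consent influenced by arm-specific content could break, so it should not be the safeguard here.

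The cost is an inner envelope, one line of instructions, two items on a form, a few lines of SAP wording and a little more analysis. The sensitivity analysis loses some precision. HCPs still receive the materials in the same mailing.
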